An increase in **total kidney volume (TKV)** precedes the decline in kidney function, which is typically delayed until the 4th decade of life in patients with ADPKD, and TKV is a prognostic biomarker of future kidney function decline¹⁸. Thus, a decrease in rate of TKV growth, as measured by **magnetic resonance imaging (MRI)** is an important indicator of kidney disease progression early in the course of ADPKD.

Curcumin is a safe, naturally occurring polyphenol found in the Indian spice turmeric that has a unique ability to activate transcription of key antioxidants, suppress inflammation, and reduce proliferation. Curcumin reduces arterial dysfunction in various rodent models of vascular dysfunction^{19,20}, and my preliminary data demonstrate that it also reduces age-associated vascular dysfunction in humans. Importantly, curcumin also slows cyst growth in kidney cells *in vitro*²¹ and *in vivo*²². Thus, curcumin is a promising **nutraceutical** to slow progression of renal and cardiovascular disease in children with ADPKD. However, there is presently **no information available** regarding the potential therapeutic benefits of curcumin to treat arterial dysfunction and slow kidney growth in this population.

Accordingly, the **primary aim** of this application is to determine the efficacy of curcumin for improving FMD_{BA} and reducing aPWV in 68 children/young adults with ADPKD. A key **secondary goal** is to obtain insight into the mechanisms by which curcumin therapy may reduce arterial dysfunction. Last, a **third exploratory aim** is to determine if treatment with curcumin slows kidney growth. These aims will be tested in a double-blind, placebo-controlled, randomized clinical trial conducted in children/young adults aged 6-25 years with ADPKD.

Hypothesis 1: Oral curcumin therapy will reduce vascular endothelial dysfunction (increase EDD) and large elastic artery stiffness in children and young adults with ADPKD as compared to placebo.

Specific Aim 1: To determine **non-invasively**: a) FMD_{BA} and b) aPWV before and after 12 months of oral curcumin (25 mg/kg/day) or placebo; and after 6 months in a sub-set of all local patients.

Hypothesis 2: The improvements in arterial function observed with oral curcumin treatment will be associated with reduced oxidative stress and inflammation.

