- Tend to ↓ the progression of TKV (adjusted for height), which can be examined further in a longer-duration, larger sample size, future R01 grant

Power Calculations and Statistical Analysis. Power calculations are based on clinically meaningful differences in the primary outcomes (FMD_{BA} and aPWV), limited published literature using curcumin in a healthy older population⁴⁴, and experience of the applicant regarding the variability of the proposed outcomes^{68,69,79}. A sample size of 27 in each group will have 90% power to detect a mean increase in FMD_{BA} of 1.5%, given a standard deviation of 2.0⁶⁸, with $\alpha = 0.025$, adjusted for two primary endpoints. Akazawa et al.⁴⁴ demonstrated in healthy post-menopausal women a ΔFMD_{BA} of +1.5% with curcumin compared to a decrease in FMD_{BA} of -0.2% in controls. Similarly, a sample size of 27/group will have 90% power to detect a mean decrease of aPWV of 100 cm/sec given a standard deviation of 125⁶⁹ with $\alpha = 0.025$, adjusted for two primary endpoints. To account for a potential dropout of 20%, 34 subjects/group will be enrolled.

A sub-sample size of 10 in each group (of 18-25 year olds) will have 89% power to detect a 50% reduction in ΔFMD_{BA} with ascorbic acid (given $\Delta FMD = +3.0 \pm 1.0\%$ with ascorbic acid in the placebo group⁶⁸), with a two-sided $\alpha = 0.05$. Aim 3 will be considered exploratory, thus power was not calculated.

Differences between groups at baseline will be assessed by an independent t-test, and a linear mixed-effects model will be fit to compare curcumin vs. placebo (independent variable) with respect to change in outcomes at 6 and 12 months (dependent variables), with covariates and potential confounders (including puberty) incorporated into the model. This approach will account for the use of multiple time points and is flexible to missing (at random) data. Although I do not expect different responses based on sex or race/ethnicity, and the study is not powered to assess these factors, stratified analysis will be performed and any trends will be noted and studied in a larger follow-up study. Dropouts will be handled using an intent-to-treat analysis.

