III. Curcumin to Treat Vascular Dysfunction

My graduate laboratory has assessed the efficacy of curcumin therapy (same company and similar normalized dose as proposed: 2,000 mg/day, Longvida™, Verdure Sciences) to reduce age-associated vascular dysfunction. Compared to placebo, FMD_{BA} was improved (**Figure 5**) in 5 healthy adults (65±3 years, 2M/3F) treated for 3 months with curcumin, as compared to placebo. The curcumin was well tolerated in all participants without any adverse effects. As aging is associated with impaired FMD_{BA} similar to ADPKD, curcumin may also reduce vascular dysfunction in children/young adults with ADPKD. Please note, aPWV and B-stiffness index were not assessed in this preliminary study, as it may require more time to change in response to an intervention.

Human Subjects

1. Risks to the Subjects

a) Human Subjects Involvement and Characteristics.

Subjects. After obtaining their written informed consent (ages 18-25) or assent (ages 6-17; plus parental consent), children and young adults aged 6-25 years with a diagnosis of autosomal dominant polycystic kidney disease (ADPKD), based on the presence of bilateral renal cysts when there is a positive family history⁵¹, and normal renal function with an estimated glomerular filtration rate (eGFR) >80 mL/min/1.73 m² (using CKid Schwartz bedside equation for ages 6-17⁵² and the CKD-EPI equation for ages 18-25⁵³) will serve as subjects. Patients will undergo screening and vascular testing at the University of Colorado Division of Renal Diseases and Hypertension Clinical Vascular Physiology Laboratory. A local contracted laboratory (Quest) and medical records will be used for screening for out of state participants. The University of Colorado Denver ADPKD Center has successfully employed this approach in previous and ongoing ADPKD clinical studies^{54,55}, including a recently completed trial by the co-mentor ([name]) in 110 children and young adults with ADPKD⁵⁶. Laboratory analysis will be performed at the University of Colorado Hospital, and mass spectrometry analyses will be performed in the iC42 Clinical Research & Development Center. Renal magnetic resonance imaging (MRI) scans will be performed at the Brain Imaging Center.

To be eligible to participate in this research, volunteers must meet the following criteria:

Inclusion Criteria:

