b) Data Safety Monitoring Plan. A data safety monitoring board (DSMB) including clinicians (a nephrologist and pediatrician) and a statistician (independent of the study investigators but part of the faculty at the University of Colorado, School of Medicine) will be formed to assess potential adverse events. These data will be prepared by the DSMB statistician, ensuring the study statistician remains blinded until the final analysis. The DSMB will meet annually to review the protocol and will follow the guidelines established by the NIH National Center for Research Resources which include: a) monitoring the progress of the protocol (e.g., reviewing subject recruitment, attrition and minority involvement) and the safety of research participants (e.g., reviewing unblinded data for safety); b) assuring compliance with requirements regarding the reporting of adverse events; c) assuring that any action that results in the temporary or permanent suspension of the protocol is reported to all the appropriate monitoring bodies (i.e., IRB, NIH, FDA, etc.); and d) assuring data accuracy and protocol compliance.

c) Reporting of Side Effects. Subjects will be instructed to report side effects to the investigator and their nephrologist, if not part of the investigative team. Any serious adverse events will be reported to the Colorado Multiple IRB, Verdure Sciences, and the FDA, in accordance with the guidelines of each of these groups. Participants who drop out of the study will be handled using an intent-to-treat analysis.

d) Exit Criteria. The primary exit criteria will include completion of the study, patient request, IRB or DSMB request, or other rationale as determined by the principal investigator or mentors. Other exit criteria are listed below. The number of subjects exiting the study and the reasons for exit will be carefully documented.

Patient Stopping Criteria:

- Withdrawal of informed consent (subject's decision to withdraw for any reason)
- Any clinical adverse event (AE), laboratory abnormality or intercurrent illness which, in the opinion of the investigator, indicates that continued participation in the study is not in the best interest of the subject
- Pregnancy
- Loss of ability to freely provide consent through imprisonment or involuntary incarceration for treatment of either a psychiatric or physical (e.g., infectious disease) illness
- Use of an investigational therapy or device other than study medication

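### The analysis text gives no test level or step-down rule for the two primary endpoints; Holm would add about 2 to 4 points of power per endpoint at the stated 90%, at the same 5% family-wise error

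*Combined protocol and SAP*

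**What the plan says.** The section Power Calculations and Statistical Analysis sizes the trial on both primary outcomes. FMD is sized for a difference of 1.5 with SD 2.0, and aPWV for 100 cm/sec with SD 125. Each has 27 per group and a stated 90% power, "with $\alpha = 0.025$, adjusted for two primary endpoints". Since 2 × 0.025 = 0.05, this is a Bonferroni split; the overall 5% is implied, not written.

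The analysis paragraph of the same section says that "a linear mixed-effects model will be fit to compare curcumin vs. placebo (independent variable) with respect to change in outcomes" at 6 and 12 months, with covariates, stratified analyses and intent-to-treat handling of dropouts. It attaches no significance level, sidedness or multiplicity procedure to FMD or aPWV, and no other section does. The only stated sidedness belongs to the Aim 2 ascorbic acid calculation, which is two-sided at 0.05.

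Both endpoints carry the primary claim. The Specific Aims set out to "determine the efficacy of curcumin for improving FMD_{BA} and reducing aPWV in 68 children/young adults with ADPKD", and Hypothesis 1 covers endothelial function and arterial stiffness together.

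**The concern.** That each endpoint will be judged at a fixed 0.025 is an inference from the sizing text, not a written rule. Two things follow.

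First, suppose one endpoint is clearly significant and the other has p = 0.03. The plan does not say outright whether the second is positive, and that should be settled before the data are seen.

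Second, if the fixed split is the rule, it gives up power for nothing in family-wise error. Holm tests the smaller p-value against 0.025 and, only if that succeeds, the larger against 0.05. The verdicts differ in one situation: one endpoint below 0.025 and the other between 0.025 and 0.05. Because Hypothesis 1 names both endpoints, the second verdict matters.

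**Working it through.** **Inputs.** From Power Calculations and Statistical Analysis: 27 per group, per-endpoint level 0.025, differences and SDs as above. Standardised effects: 1.5/2.0 = 0.75 (FMD) and 100/125 = 0.80 (aPWV). Assumed, because the documents do not give them: two-sided t-tests at one time point, and a correlation of 0 to 0.9 between the two test statistics.

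**Step 1. The plan's 90%.** The noncentrality is d × √(27/2), with df = 52. This is 0.75 × 3.674 = 2.756 for FMD and 0.80 × 3.674 = 2.939 for aPWV. Power from the noncentral t:

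| Endpoint | two-sided 0.025 | two-sided 0.05 (= one-sided 0.025) |
|---|---|---|
| FMD | 67.3% | 77.2% |
| aPWV | 73.5% | 82.2% |

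The stated 90% does not reproduce for the between-group comparison. That shortfall is a separate and larger matter; here it means that the gain must be shown under both conditions. Exactly 90% at two-sided 0.025 needs d = 0.983, which gives 94.3% at two-sided 0.05.

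**Step 2. Formula for the gain.** For endpoint i, with j the other endpoint:

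gain = P(0.025 < p_i ≤ 0.05 and p_j ≤ 0.025).

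At zero correlation this is a product that can be checked by hand:

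- Stated 90%: (94.3 − 90.0) × 0.900 = 3.9 points.
- Plan inputs, FMD: (77.2 − 67.3) × 0.735 = 7.3 points.
- Plan inputs, aPWV: (82.2 − 73.5) × 0.673 = 5.9 points.

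**Step 3. Other correlations.** Simulation of correlated two-sample t-statistics, 2,000,000 runs per case, both effects real.

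At the stated 90% per endpoint:

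| Correlation | Per endpoint, split → Holm | Both positive, split → Holm | Trials gaining a second positive | At least one positive (either rule) |
|---|---|---|---|---|
| 0 | 90.0 → 93.9% | 81.0 → 88.8% | 7.8% | 99.0% |
| 0.3 | 90.0 → 93.5% | 82.1 → 89.2% | 7.1% | 97.9% |
| 0.5 | 90.0 → 93.3% | 83.2 → 89.7% | 6.5% | 96.9% |
| 0.8 | 90.0 → 92.6% | 85.6 → 90.7% | 5.2% | 94.5% |
| 0.9 | 90.0 → 92.2% | 86.9 → 91.2% | 4.4% | 93.2% |

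A separate normal-approximation calculation gives +3.7 points at correlation 0 and +2.1 at 0.9, in agreement.

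On the plan's own differences and SDs:

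| Correlation | FMD, split → Holm | aPWV, split → Holm | Trials gaining a second positive |
|---|---|---|---|
| 0 | 67.3 → 74.6% | 73.5 → 79.4% | 13.2% |
| 0.5 | 67.3 → 73.8% | 73.5 → 78.1% | 11.2% |
| 0.9 | 67.3 → 73.1% | 73.5 → 76.1% | 8.4% |

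**Step 4. Sensitivity.**

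- *Covariates.* If adjustment cuts the residual SD by 10, 20 or 30% (assumed; correlation 0.3), the gain on plan inputs is 6.1, 4.6 or 2.4 points for FMD and 4.4, 3.0 or 1.4 for aPWV.
- *Only one effect real.* That endpoint gains 0.0–0.3 points. The false-positive chance on the other rises from 2.5% to 3.8–4.8%, within 5% family-wise.
- *Neither effect real.* Family-wise error is 5.0% at correlation 0, falling to 3.7% at 0.9, the same for both rules.
- *Sidedness.* If 0.025 was meant one-sided, one-sided Holm (0.025, then 0.05) adds 2.3–4.2 points at 90%. Moving to two-sided Holm at the same time would lower power instead, from 90% to about 87–89%.

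**The case against.** The plan does adjust for two primary endpoints, and states the adjusted level twice under the same heading as the analysis. A reader may fairly take 0.025 as the test level, and Bonferroni at 0.025 is valid with simple matching intervals. On that view this is a preference between two valid methods.

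The gain is also small and conditional. It needs both effects to be real, it leaves the chance of at least one positive endpoint unchanged, and the evidence for aPWV is thin. The plan's preliminary results for curcumin say "aPWV and B-stiffness index were not assessed in this preliminary study, as it may require more time to change in response to an intervention". If only FMD responds, Holm mainly raises the false-positive chance on aPWV. Correlation is not given, and the planned analysis is a covariate-adjusted mixed model, not a pair of t-tests. Holm also does not repair the gap between the stated 90% and the roughly 67% and 73% that the inputs give.

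All of this stands as a limit on size, and it is why the point is minor. It does not remove the point. The analysis paragraph still has no rule for a second endpoint with p between 0.025 and 0.05. Holm never rejects less than the split, holds 5% family-wise under any dependence, and costs almost nothing to adopt. The unknown correlation changes the figure little: at −0.3 the gain at 90% power is about 4.1 to 4.2 points.

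**Conclusion.** The concern holds, as a minor one. No test level, sidedness or step-down rule is written for the primary analyses. If the Bonferroni split is the intended rule, Holm adds 2.2 to 3.9 points per endpoint at the stated 90% power. On the plan's own inputs it adds 5.8 to 7.3 points for FMD and 2.6 to 5.9 for aPWV. These figures assume both effects real, two-sided t-tests with 27 per group, and correlations from 0 to 0.9. The benefit is confined to the second claim.

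**What to change.** Add to the analysis paragraph, before unblinding, wording such as:

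> FMD and aPWV at month 12 will be tested by the Holm procedure at a family-wise alpha of 0.05 (smaller p-value against 0.025; if significant, the other against 0.05). The Holm test decides significance; the 97.5% confidence intervals are descriptive.

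As a separate decision, state whether these tests are one- or two-sided, keeping whichever sidedness the 0.025 was meant to have. Two-sided is the natural reading beside the two-sided Aim 2 calculation. Keep 0.025 for sample-size planning. If the fixed split is preferred for its matching intervals, write that rule into the analysis paragraph instead.

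The cost is two or three sentences and no extra patients. The Data Safety Monitoring Plan helps with timing, since unblinded safety data go through the DSMB statistician, "ensuring the study statistician remains blinded until the final analysis". Two downsides should be accepted knowingly. An endpoint with p between 0.025 and 0.05 can be declared positive while its 97.5% interval includes zero. If only one endpoint truly responds, the false-positive chance on the other rises from 2.5% to about 4–5%, within the 5% family-wise limit.

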Subjects. After obtaining their written informed consent (ages 18-25) or assent (ages 6-17; plus parental consent), children and young adults aged 6-25 years with a diagnosis of ADPKD, based on the presence of bilateral renal cysts when there is a positive family history⁵¹, and normal renal function with an estimated glomerular filtration rate (eGFR) >80 mL/min/1.73 m² (using CKid Schwartz bedside equation for ages 6-17⁵² and the CKD-EPI equation for ages 18-25⁵³) will serve as subjects. Patients will undergo screening and vascular testing at the University of Colorado Denver Division of Renal Diseases and Hypertension Clinical Vascular Physiology Laboratory, which is part of the Clinical Research Unit. A local contracted laboratory (Quest) and medical records will be used for screening for out of state participants. The University of Colorado Denver ADPKD Center has successfully employed this approach in previous and ongoing ADPKD clinical studies^{54,55}, including a recently completed trial by the co-mentor ([name]) in 110 children and young adults with ADPKD⁵⁶. Laboratory analysis will be performed at the University of Colorado Hospital or by Quest, and mass spectrometry analyses will be performed in the iC42 Clinical Research & Development Center. Renal magnetic resonance imaging (MRI) scans will be performed at the Brain Imaging Center. Major inclusion/exclusion criteria are presented in the table below (Table 1). Those who drop-out/do not complete the study will be encouraged to undergo an end-of study visit which will include identical measurements to the ones planned for session 5.

Table 1 Inclusion Criteria	Exclusion Criteria

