Study Modifications to Account for COVID-19 Outbreak. On account of COVID-19 and Institutional policies in place regarding work-related travel, the length of treatment of participants in may be extended due to extenuating circumstances. The end-of-study visit may be delayed due to concerns over air travel, in which case participants will be asked to continue taking the curcumin/placebo, as they have been doing for the past year, and we will reschedule their end-of-study visit at the earliest time point that seems appropriate (hopefully within a couple of months). We will obtain in-person data at this time, but will ask participants to go to our contract laboratory for the clinical labs at the planned 12 month time point if possible. We do not see any additional risk posed to participants by extending their treatment period, as curcumin already has a very favorable safety profile.

Summary of risks associated with curcumin. Based on preliminary studies (see below) and an extensive review of literature, the proposed doses of curcumin are both physiologically relevant and predicted to be well-tolerated by the great majority of study participants. The primary risk associated with curcumin supplementation is the possibility of temporary/transitory gastrointestinal distress (flatulence, constipation, diarrhea, nausea) in a very small percentage of individuals ^{61,65,67}.

Measurements.

Screening Measures. Subjects will undergo a medical history and physical exam, including growth parameters and Tanner staging ⁷⁴⁻⁷⁶, aspartate aminotransferase (AST), alanine aminotransferase (ALT), and a pregnancy test for all female participants of possible childbearing potential (Tanner Stage 2 or higher). Serum creatinine will be measured for determination of eGFR using the CKid Schwartz bedside equation for ages 6-17 ⁵² and the CKD-EPI equation for ages 18-25 ⁵³. A local contracted laboratory (Quest) and medical records will be used for out of state participants. EMLA cream may be used as needed to numb the skin prior to drawing blood.

Measures of Adherence and Safety:

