Adherence. As we expect ~50% of all participants to be from out of state, progress will be reviewed with a monthly phone inquiry of medication supply. Please note, due to the long history and prestige of University of Colorado PKD Center studies, our families have tremendous relationships with our research staff (i.e. investigators and research coordinators). The co-mentor, [name], has successfully employed this approach in previous clinical trials in children/young adults with ADPKD that have included ~50% out of state patients ^{54,56}. We expect the minimal side-effects associated with curcumin to favor adherence. Participants will have powder mailed every 3 months and will also be asked to mail back the bottle for a volume check.

Safety Checks. While adverse events are not anticipated, a safety questionnaire will be administered over the phone monthly. Serum creatinine, ALT and AST will be measured after 1, 6, and 12 months, and for those out of state, will be performed at a local contracted laboratory (Quest). Home pregnancy tests will be required monthly for all girls of possible childbearing potential (\geq Tanner Stage 2). All subjects will be given a digital blood pressure monitor (A&D Medical, UA767) with an appropriately sized cuff and the subject/parent will be instructed in its use. Home blood pressures will be taken monthly and reported during phone safety checks. This approach has been successfully employed previously by the co-mentor, [name] ^{54,56}.

Plasma Curcumin Concentrations will be assessed at baseline and 12 months by liquid chromatography-tandem mass spectrometry (LC-MS/MS) at the University of Rhode Island ⁷⁷. Additionally, curcumin concentrations will be measured by the in red blood cells, the buffy coat, and plasma with the addition of citrate to prevent the degradation of metabolites.

Randomization will be performed by the statistician, using a blocked randomization sequence, with stratification by age group (6-13 or 14-25 yrs).

Outcome Measures. The following measurements will be made at baseline and after 12-months of treatment:

Primary (Functional) Outcomes (Specific Aim 1)

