Brachial Artery FMD and Endothelium-Independent Dilatation. FMD_{BA} will be determined using high-resolution ultrasonography (Toshiba Xario 200) as described originally by Celermajer et al. ⁷⁸ and used recently by the applicant ^{68,79,80}. FMD_{BA} is a widely used, non-invasive method inducing reactive hyperemia to assess endothelium-dependent dilation. It is validated in children ^{78,81} and is mainly dependent upon NO production ^{82,83}. Brachial artery endothelium-independent dilation will be determined in the sub-group of participants aged 18-25 yrs by measuring brachial artery dilation for 10 minutes after administration of sublingual nitroglycerin (0.4 mg) ^{67,84,85}. This assessment is key to the interpretation that any improvements in dilation are indeed dependent upon endothelial production of NO rather than improved smooth muscle relaxation to NO ⁸⁶. The use of nitroglycerin is currently safely employed in an NIH-funded, IRB-approved protocol in adults with ADPKD at the University of Colorado Denver. A commercially available software package (Vascular Analysis Tools 5.8.1, Medical Imaging Applications) will be used to acquire and analyze ECG-gated brachial artery diameters. Doppler blood flow velocity will be obtained for estimation of shear rate, which will be entered as a covariate if indicated ⁸⁷⁻⁸⁹.

Aortic Pulse-Wave Velocity. aPWV will be determined as described in detail previously by applicant ^{69,90} and validated in children ^{71,91}. Briefly, a transcutaneous custom tonometer (Noninvasive Hemodynamics

Workstation, Cardiovascular Engineering Inc.) will be positioned at the carotid and femoral arteries to non-invasively assess aPWV, as distance/time between the foot of the arterial waveforms⁹². As a secondary index of arterial stiffness, ultrasound imaging of the carotid artery will also be performed for calculation of carotid artery compliance and the β -stiffness index (in conjunction with tonometry), as described previously^{96,97}. The images will also be assessed for measurement of carotid artery intimal-medial thickness (IMT), which is used in the calculation of carotid artery compliance and the β -stiffness index.

Outcomes for Specific Aims 2 (Only in the sub-group aged 18-25 years (except for urinary markers))

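### The primary mixed model for change does not commit to the baseline value of the endpoint or to the randomisation age stratum; naming both is a cheap precision gain of uncertain size

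*Combined protocol and SAP*

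**What the plan says.** The section Power Calculations and Statistical Analysis holds the only description of the primary analysis. A linear mixed-effects model compares the arms "with respect to change in outcomes at 6 and 12 months (dependent variables), with covariates and potential confounders (including puberty) incorporated into the model". Baseline appears there in one other role: a t-test of the arms at baseline. Because the response is change, the baseline value is not part of the response vector either.

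Under Randomization, allocation is made "using a blocked randomization sequence, with stratification by age group (6-13 or 14-25 yrs"). The statistical section does not mention that stratum.

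Under Experimental Design, Session 2 measures FMD and aPWV in all subjects before treatment, so both baseline values are available.

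On size, the plan states "A sample size of 27 in each group will have 90% power" for a 1.5% difference in FMD (SD 2.0), and the same for a 100 cm/sec difference in aPWV (SD 125). Alpha is 0.025 per endpoint. The text does not say whether these are SDs of change or single-visit SDs, whether 0.025 is one- or two-sided, or what correlation between visits is expected.

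**The concern.** A change score subtracts the whole baseline value, which is the most precise use of baseline only if the regression of the month-12 value on baseline has slope one. With measurement noise and biological variation the slope is usually lower, and regression to the mean is left in the residual. Putting baseline in the model removes it. A model limited to treatment and puberty would therefore estimate the treatment difference less precisely than the collected data allow.

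The stratum raises a related but weaker point. Stratified allocation balances the arms on age group, and an analysis that leaves age group out does not credit that balance in its standard error. With about 54 evaluable subjects and two co-primary endpoints, even modest precision is worth having.

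**Working it through.** **Inputs from the plan.** 27 evaluable per group; FMD difference 1.5, SD 2.0; aPWV difference 100, SD 125; alpha 0.025.

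**Assumptions.** Alpha two-sided (one-sided would start at 77% for FMD and 82% for aPWV); SDs are SDs of change; equal variance at baseline and month 12; r shown as a range.

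**Step 1: the plan's own figure.** Non-centrality is difference / (SD × √(2/27)), with 52 df and critical t 2.308.
- FMD: 1.5 / (2.0 × 0.2722) = 2.756, power 67.3%.
- aPWV: 100 / (125 × 0.2722) = 2.939, power 73.5%.

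The stated 90% is not reproduced. That is a separate issue, so results are also given from a 90% start (a standardised difference of 0.983).

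**Step 2: variance after adding baseline.** With visit variance σ²:
- unadjusted change: 2σ²(1−r)
- change given baseline: σ²(1−r²)
- ratio: (1−r²) / [2(1−r)] = (1+r)/2, or 0.65, 0.75, 0.85 and 0.95 at r = 0.3, 0.5, 0.7 and 0.9.

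**Step 3: cost of estimating the slope.** One degree of freedom is lost (51 df). Chance imbalance in one covariate multiplies the variance by about (54−3)/(54−4) = 1.02. Example, FMD at r = 0.5: 1.5 / (2.0 × √(0.75 × 1.02 × 2/27)) = 3.151, power 79.7%.

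| Month-12 contrast | No baseline | r = 0.3 | 0.5 | 0.7 | 0.9 |
|---|---|---|---|---|---|
| FMD | 67% | 86% | 80% | 74% | 69% |
| aPWV | 73% | 90% | 85% | 80% | 75% |
| 90% start | 90% | 98% | 96% | 94% | 91% |

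Without the 1.02 factor the entries are up to about 1 point higher.

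**Step 4: check with puberty in both models.** In simulation (12,000 trials, Monte Carlo error about 0.4 points), adding baseline and a stratum that explains nothing to treatment plus puberty gave net gains at the same r of 18/11/6/1 points (FMD), 16/11/5/1 (aPWV) and 8/6/4/0 from a 90% start.

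**Step 5: the other reading of the SDs.** If they are single-visit SDs, the SD of change is s√(2(1−r)) and the adjusted SD is s√(1−r²). Leaving out the imbalance factor, FMD goes from 51/67/89% to 72/81/94% and aPWV from 57/73/93% to 78/86/96% at r = 0.3/0.5/0.7. At r = 0.9 power is about 100% either way.

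**Step 6: the stratum alone.** It costs under 1 point if it explains nothing. At r = 0.7, if it explained an assumed 5, 10 or 20% of the variance left after baseline, it would add about 1, 1.5–2.5 or 3–5 points.

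**Step 7: worst case.** If neither covariate is prognostic, the variance rises by about 51/49 = 1.041 with 50 df. Power falls from 67.3 to 65.2% (FMD), from 73.5 to 71.5% (aPWV) and from 90.0 to 88.7% (90% start). Simulation gave 65.1, 71.4 and 88.6%.

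**The case against.** **The covariate list is open.** A reader might infer that the plan excludes baseline or that its analysis is biased. Neither follows. Puberty is given as one example, nothing rules the other terms out, and unadjusted change is unbiased under randomisation. What stands is that the plan does not commit to them.

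**The gain may be small.** It runs from almost nothing to nearly 20 points, depending on r and on the type of SD, and the larger figures start from 67% and 73% rather than the stated 90%. This is right, and is why a range is shown.

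**The model may pool 6 and 12 months.** If it estimates one effect over both visits, fully present by month 6, the unadjusted pooled analysis has 74.6% (FMD), 80.4% (aPWV) or 94.1% (90% start), taking half the sample at month 6 and equal correlation between visits. Moving to a month-12 contrast as well as adjusting would then gain nothing at r = 0.7 and lose at r = 0.9. That counts against bundling the two changes, not against the covariates. With pooling kept and baseline added, FMD is 94.3/89.0/83.2/77.4% and aPWV 96.6/92.8/88.0/82.9% at the four values of r (imbalance factor left out).

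**The stratum case is thin.** Age group overlaps puberty, and the rationale for treatment duration says that aPWV changes across puberty while available data suggest that FMD does not. This stands.

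**Late choice of covariates is partly guarded against.** Under Experimental Design, those who analyse the data are blinded, and the Data Safety Monitoring Plan keeps the study statistician blinded until the final analysis. That lowers the risk of a choice driven by the results, though it does not fix the list.

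**Conclusion.** The point holds as a minor, recommended improvement. Baseline carries most of the gain: about 19/13/7/2 points for FMD and 17/12/7/2 for aPWV at r = 0.3/0.5/0.7/0.9 (table entries less the 67% and 73% starts), and about 8/6/4/1 from a 90% start. These figures assume SDs of change, two-sided 0.025 and equal visit variances. The stratum may add nothing; it is supported mainly because the analysis should reflect how subjects were allocated.

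Three stronger readings are not supported:
- **Adjustment rescues the stated power.** With SDs of change it reaches 90% only if r is at most about 0.16 (FMD) or 0.32 (aPWV), and slightly less after the imbalance cost. The shortfall needs its own answer.
- **The primary time point is undefined.** Specific Aim 1 sets 12 months for everyone "and after 6 months in a sub-set of all local patients", and Outcome Measures says "The following measurements will be made at baseline and after 12-months of treatment". Month 12 is implied, though the model sentence lists both visits.
- **Other open rules are part of this flaw.** Shear rate, "which will be entered as a covariate if indicated", and the handling of delayed or early end-of-study visits are unstated details. Settling them involves trade-offs, and the case for baseline and stratum does not depend on them.

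**What to change.** In Power Calculations and Statistical Analysis, add:

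> The planned linear mixed model for change will include the baseline value of the endpoint (with baseline-by-visit) and the randomisation age stratum (6-13, 14-25) as fixed effects, in addition to puberty.

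The sentence should be in place before unblinding. It keeps the planned model, response, visits and alpha. Baseline FMD and aPWV are already measured in all subjects and the stratum is known from randomisation, so no new data are needed. The cost is one sentence of plan text and, at worst, about 2 points of power if neither covariate predicts change.
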